An initial dosage of the blood levels of AA, EPA and DHA (and relative ratio) will be carried out by capillary sampling and application of a few drops of blood on absorbent paper for all subjects. Fatty acids are measurable in whole blood, with a lipidogram, in which each component of FFA is selectively differentiated, and then quantified the individual fractions. In particular we will evaluate the ratio between 20: 4 Ω -6 arachidonic acid (AA), precursor of pro-inflammatory cytokines, and EPA, precursor of anti-inflammatory cytokines; this ratio represents a balance between the effector pre-metabolites of inflammation, which determine the apoptotic degeneration of β -cells, and the anti-inflammatory ones, which preserve a cellular share with an insulin secretive function. This value AA / EPA <3 is proposed in Literature for adults or patients with other diseases, but has also been used for children.

The measurement will be carried out free of charge at the Department of Pharmacological and Biomolecular Sciences (DiSFEB), Faculty of Pharmaceutical Sciences, University of Milan.

An assessment of the dietary intake of EPA and DHA fatty acids will be carried out for all the subjects included in the study through an interview with the dietician and the compilation of a frequency food questionnaire. The collection of the food questionnaire will take place at the time of enrollment (T0) and 12 months after supplementation with omega 3. All healthy control subjects will be submitted to the food questionnaire. Nutritional indications will be given to all families in order to optimize an optimal dietary introduction of fatty acids as indicated by the LARNs.

Supplementation

The intervention under study is only the administration of omega-3, to all patients with onset in recent years (2014-2018) with a contribution of 60 mg / kg / day of the sum of EPA and DHA (corresponding respectively to acid eicosapentenoico and docaesoenoico). The AA / EPA ratio will be monitored (arachidonic acid, Ω -6 / eicosapentenoic acid Ω -3), to reach the optimal range <3 , as indicated in the literature.

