The chosen preparation will be omega-3, of extraction from fish, with a high concentration and purified to exclude mercury and lead, commercially available in stores and supermarkets. EnerZona. Equipe Enervit Srl will provide free Ener Zone, in capsules, from EPA 400 mg + DHA 200 mg, or capsules from EPA 200 mg + DHA 100 mg, or liquid solution, for subjects unable to swallow capsules or intolerant gluten capsules themselves; this will allow us to provide precise delivery and the same preparation to each patient.

All of our patients are supplemented with vitamin D. As vitamin D also has an immunomodulatory role it will be monitored in the study, and being frequently low at onset will be given at 1000 IU / day, as indicated in prophylaxis for children and adolescent; its level [as 25 (OH) D] will be controlled to reach the optimal values (established by Endocrine and other scientific societies) of 40-50 ng / ml, and possibly increased or reduced.

Inclusion criteria:

All children with autoimmune T1D, debuted in the years selected at the Pediatric Clinic of Novara. Some children with T1D in the wake of the published anecdotal case, have already spontaneously begun to supplement with omega 3, and will be excluded from the study. We have primarily considered our series of children with T1D onset according to the ADA, ISPAD and SIEDP criteria of the years 2015, 2016 and 2017, since insulin secretive activity persists for at least two years from the onset.

Exclusion criteria:

pathologies such as:

- coagulation defects
- renal diseases (nephrotic syndrome, calculosis, renal cysts, etc.)
- sarcoidosis, histoplasmosis

01/01/2017

- endocrinological diseases (hyperparathyroidism)
- tumoral pathologies or tuberculosis

Gluten intolerance (CD) or thyroiditis in T1D are not exclusion criteria.

Chronology of investigations and time of execution of the study

T.0 Signature of informed consent. Baseline auxological and metabolic evaluation (IU / Kg / day exogenous insulin) by means of examination, assessment of dietary intake through food questionnaire and interviews with dietician, blood tests (vitamin D, AA / EPA, C-peptide, basal glycemia, glycated hemoglobin, lipid profile, coagulation). Discharge of glucometer data for glycemic variability. Start supplementation with vitamin D, in case of deficiency, if subject not already supplemented. Begin supplementation with EPA + DHA, in case of deficiency, if willingness to recruit.

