T.3 at 3 months from the beginning of the supplementation, only for the subjects supplemented with omega 3. Auxological and metabolic evaluation (IU / Kg / day exogenous insulin) by examination, blood tests (AA / EPA, C-peptide, basal glycemia, glycated hemoglobin, lipid profile, coagulation). Discharge of glucometer data for glycemic variability.

T.6 to 6 months from start of supplementation, only for subjects supplemented with omega 3. Auxologic and metabolic evaluation (IU / kg / exogenous insulin) by examination, blood tests (AA / EPA, C-peptide, basal blood sugar, glycated hemoglobin, lipid profile, coagulation). Discharge of glucometer data for glycemic variability.

T.12 At 12 months from the beginning of the study, will be re-evaluated for all subjects, all the previous auxological, metabolic and biochemical parameters and a new evaluation of the dietetic dike of fatty acids will be carried out.

Study security and caution of the subject included

The safety of the therapy with supplements is reflected in the extensive experience of using cod liver oil which in the past has been a routine supplement for children for several years.

High doses of Ω -3 over 5 g / day could result in a longer bleeding time, which is why coagulation monitoring is required, even if supplementation is required at doses of less than 5 g / day. With the use of Ω -3 a reduction of triglyceride levels is observed, which could represent a clinical advantage for the subject and a precise therapeutic objective often sought by the practitioners. A triglyceride evaluation will be performed pre-supplementation and at 12 months from the beginning of the same.

Financial resources and expected costs

01/01/2017

Enervit supplies Ener Zone Omega 3 RX in capsules containing each EPA 400 mg + DHA 200 mg and in liquid formulation for younger children and / or with concomitant celiac disease. Ascensia Diabetes Care supplies Conturnext USB and Conturnext strips, to allow frequent blood glucose measurements, with accuracy and precision.

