The blood chemistry tests are part of the normal T1D treatment routine. The dosage of the different metabolic and hormonal parameters at the time T1 will be borne by the Pediatric Clinic. The AA / EPA report will be determined by the Department of Pharmacological and Biomolecular Sciences DiSFEB, Faculty of Pharmaceutical Sciences of the University of Milan free of charge. Other possible findings as coagulation will be calculated as expenditure "study use" of the Pediatric Clinic.

DATA PROTECTION

to. Blood samples collected on Guthrie cardboard sent to Milan will be collected with the informed consent of the parents.

b. For the protection of the subject and clinical data, withdrawals will be identified with a code.

c. The clinical data will be managed by clinical referents inside Pediatrics ([name], [name]) and the name of the subject will be identified by initial name and surname

d. The withdrawals will be stored in the Laboratory of Milan Pharmacy University of the Maggiore Hospital under the exclusive control of the laboratory referents ([name])

Statistic analysis

The data will be expressed as a mean \pm SD. For continuous variables, the variations between the groups are compared by means of the averages calculated with the non parametric Wilcoxon and Mann-Whitney U tests. The variability of the biochemical parameters over time will be evaluated by means of tests for repeated measurements. A correlation analysis will be performed with the Pearson correlation test, after adequate logarithmic transformation of the parameters when necessary. Multiple regression analysis will be used to evaluate associations between variables. Statistical significance will be assumed for values of $p < 0.05$. All statistical analyzes will be performed with the SPSS program for Windows version 22.0 (SPSS INC; Chicago, IL, USA).

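### No visit records bleeding, other adverse effects or stopping of omega-3, and the coagulation tests meant to cover the one named harm are not specified

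*Protocol*

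**What the plan says.** The protocol section *Study security and caution of the subject included* rests safety on past use of a related product: "The safety of the therapy with supplements is reflected in the extensive experience of using cod liver oil". It then names one harm. Omega-3 at more than 5 g/day "could result in a longer bleeding time, which is why coagulation monitoring is required", and the sentence continues "even if supplementation is required at doses of less than 5 g / day". The only other effect discussed there, lower triglycerides, is presented as a benefit.

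Under *Supplementation*, the intervention is given "with a contribution of 60 mg / kg / day of the sum of EPA and DHA". No daily maximum is stated. The preparation is a purified, high-concentration fish-oil product. Coagulation defects head the list of exclusion criteria.

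*Chronology of investigations and time of execution of the study* lists coagulation among the tests at T.0 ("blood tests (vitamin D, AA / EPA, C-peptide, basal glycemia, glycated hemoglobin, lipid profile, coagulation"), T.3 ("blood tests (AA / EPA, C-peptide, basal glycemia, glycated hemoglobin, lipid profile, coagulation") and T.6 ("basal blood sugar, glycated hemoglobin, lipid profile, coagulation"). T.12 includes it by repeating all earlier biochemical parameters. The general variable list in *Subjects and Methods* also includes it at all four times. No section says which coagulation tests are meant. The protocol's *Statistic analysis* section and the SAP contain no safety or discontinuation analysis.

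**The concern.** The plan names a clinical harm and answers it with an unspecified laboratory item. It does not provide for asking the child or family about that harm. Nosebleeds or bruising in a supplemented child might be mentioned to a clinician, but nothing requires anyone to ask or to write it down. The same holds for any other adverse effect.

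Two things are at stake. First, this is a preliminary study in children of a concentrated product dosed by body weight. Basic tolerability is a result that readers will expect, and the plan produces no data for it. Second, a child who stops omega-3 leaves no recorded date or reason. That child's T12 values could then be analysed as values on supplementation, and stopping because of side effects could not be told apart from stopping for other reasons.

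**Working it through.** The plan states no event rate, sample size or safety figure on this point, so there is nothing to reproduce. The check compares the lists and does one piece of arithmetic.

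**1. What each visit collects** (*Chronology of investigations*, with the variable list in *Subjects and Methods*)

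| Visit | Who | Content | Coagulation | Bleeding or adverse effects | Date and reason for stopping |
|---|---|---|---|---|---|
| T0 | all | examination, diet, bloods, glucometer | listed | not listed | not applicable |
| T3 | supplemented only | examination, bloods, glucometer | listed | not listed | not listed |
| T6 | supplemented only | examination, bloods, glucometer | listed | not listed | not listed |
| T12 | all | repeat of earlier parameters, diet | by reference | not listed | not listed |

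Planned records of bleeding or adverse effects: 0 at 4 visits, 3 of which come after the start of supplementation. Planned records of stopping: 0 at those 3 visits. The examination is described as auxological and metabolic. Glucometer downloads may contain low glucose values, but they are collected for glycaemic variability, not as adverse events.

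**2. Does the monitoring match the named harm?** The harm is a longer bleeding time and the control is coagulation. Because the tests are not named, and no process for reviewing a result is given, the documents neither show that the control would detect the harm nor show that it would not. The clinical sign of the harm, bleeding, is not asked about.

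**3. Does the dose stay under 5 g/day?** Inputs: 60 mg/kg/day of EPA + DHA (*Supplementation*) and 5 g/day (safety section). I take the 5 g to be counted on the same EPA + DHA basis; the documents do not say.

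Daily dose in g = 60 × weight in kg / 1000

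- 30 kg: 1.8 g/day
- 60 kg: 3.6 g/day
- 80 kg: 4.8 g/day
- 85 kg: 5.1 g/day

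Weight at which the dose equals 5 g/day = 5000 / 60 = 83.3 kg.

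Below about 83 kg the two statements agree. Above it they conflict, because no maximum is stated. The documents give no weights, so the number of children affected is unknown.

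**4. Can exposure be recovered another way?** AA/EPA is measured at T0, T3 and T6, and at T12 with the earlier biochemical parameters. A ratio that drifts back may suggest that a child has stopped. It gives neither the date nor the reason.

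**The case against.** The strongest reply is that the protocol ties the harm to doses above those it intends to use, monitors coagulation anyway, and excludes children with coagulation defects. Safety is not a stated objective of this preliminary study. The blood chemistry is part of routine diabetes care, so study visits need not be the only contacts. All of this stands and lowers the expected risk. It does not supply a record of adverse effects or of stopping.

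Three stronger readings are tempting and are not supported.

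- *The coagulation panel cannot detect a longer bleeding time.* A reader might assume that it consists of clotting times only. The documents do not define it, so this would be an assumption. What they support is that detection has not been shown.
- *Coagulation is required in one place and optional in another.* The sentence "Other possible findings as coagulation will be calculated as expenditure" might suggest this. It is budget wording about who pays. Coagulation is already scheduled at all four visits, so there is nothing to make fixed.
- *Children who stop will be counted as exposed without anyone knowing.* AA/EPA gives a partial indication, so the right word is could, not will.

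The consent pages and a block of the protocol's background text were not available to me. Instructions on reporting side effects could be there, although the background is an unlikely place for them.

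**Conclusion.** The point holds as a gap in recording, not as evidence of a hazard. The plan schedules no record of bleeding, other adverse effects or discontinuation at any of its four visits, leaves its coagulation tests unnamed, and has no safety summary. Followed exactly, it yields no tolerability result and no dates or reasons for stopping. Its only safety results would be coagulation values whose relevance to the named harm has not been shown.

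A reader might infer that bleeding is a likely risk at the study dose. The documents do not support that: they attach the harm to more than 5 g/day, and 60 mg/kg/day stays below that level up to about 83 kg. Above that weight the *Supplementation* and safety sections contradict each other and must be reconciled. The 83 kg figure assumes that the 5 g is counted as EPA + DHA.

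The change is worth making because the participants are children and the correction is cheap. It does not call the metabolic aims into question. The conclusion assumes that the visit lists are complete as written.

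**What to change.** 1. At the existing T0, T3, T6 and T12 visits, add a short standard record of bleeding symptoms, any other adverse event and, after the start, the date and reason if omega-3 was stopped. The T0 entry gives the baseline.
2. Name the coagulation tests that are done.
3. Add to the SAP a descriptive summary of bleeding, other adverse events and discontinuations, with AA/EPA as supporting information on exposure. Do not infer bleeding safety from the coagulation results alone.
4. Reconcile the per-kg dose in *Supplementation* with the below-5 g/day statement in the safety section. How this is resolved, and how findings are managed clinically, is for the investigators.

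Cost: one short form and a few minutes per visit, with no new visit or procedure. The limitation is that the reports are unblinded and, at T3 and T6, have no comparator because only supplemented children attend. They can describe tolerability but cannot attribute events to omega-3.

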Usually the honeymoon phenomenon is exhausted within a year, even if a residual amount of secretion persists at least up to two years from the onset. The endogenous insulin secretion is quantifiable as C-peptide, which represents the conjugation peptide between chain A and B of pro-insulin, which after free cleavage in the portal circle molecules of C-peptide and insulin in molar ratio 1: 2. Unlike insulin that is rapidly degraded in the liver and tissues, the C-peptide passes the liver and is filtered by the unchanged renal glomeruli in the urine. C-peptide is not present in exogenous insulin of pharmacological origin. The endogenous insulin secretion is quantifiable as C-peptide. A persistence of C-peptide (also dosages 0.2 ng / ml) reduces the risk of complications, improves the metabolic compensation and reduces the number of hypoglycemic episodes, so at least one of its maintenance would be an important objective to preserve.

01/01/2017

The study is preliminary and aimed at identifying whether a therapy with Ω -3 could be of support in T1D especially in the first years of illness, when a persistence of a residual β -cell mass is presumable and it is possible to act better on the pro-inflammatory component (insulinitis).

Purpose of the study

The aim of the study is to evaluate whether a controlled administration of vitamin D and Ω -3, in the early years of the onset of T1D, can preserve the residual β -cell mass, evaluable with a reduced insulin need for a long time, with a persistent level of C-peptide, a lower glycemic variability compared to children who do not carry out this supplementation.

Secondary assessment is to perform a baseline assessment of the AA / EPA ratio in children with type 1 diabetes.

Subjects and Methods

The subjects will be recruited at the Diabetology Clinic of the Pediatric Clinic of the AOU "Maggiore della Carità" of Novara.

In particular, two groups of subjects will be included, subject to the signing of the informed consent:

1°,2°,3° the groups, with T1D onset in 2014, 2015, 2016, retrospectively were evaluated as historical controls before 2017.

4 group°: all children with T1D with disease onset in the years 2017, will receive omega 3 supplement (EPA + DHA 60 mg / kg / of), and will be compared from a metabolic point of view (in particular for the needs of insulin and glycated hemoglobin) according to the scheme outlined with the pre-supplementation data, deduced from the medical records retrospectively.

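### The 60 mg/kg/day dosing rule has no maximum, so above 83.3 kg it breaks the Protocol's own statement that doses stay below 5 g/day

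*Protocol*

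**What the plan says.** **Dose.** The Supplementation section of the Protocol gives omega-3 to children with recent onset "with a contribution of 60 mg / kg / day of the sum of EPA and DHA". Subjects and Methods says of the 2017-onset group that they "will receive omega 3 supplement (EPA + DHA 60 mg / kg / of", and the SAP repeats this under Statistic analysis. None of the three places gives a maximum daily amount.

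**Safety statement.** Under Study security and caution of the subject included, the Protocol says "High doses of Ω -3 over 5 g / day could result in a longer bleeding time". It gives this as the reason for monitoring coagulation, and adds that monitoring applies "even if supplementation is required at doses of less than 5 g / day".

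**Who can be dosed.** The Inclusion criteria admit "All children with autoimmune T1D, debuted in the years selected at the Pediatric Clinic of Novara". No weight, BMI or upper age limit is given. The Exclusion criteria list "coagulation defects".

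**Product.** It is supplied "in capsules, from EPA 400 mg + DHA 200 mg, or capsules from EPA 200 mg + DHA 100 mg", or as a liquid.

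**Monitoring.** Coagulation is among the blood tests at T0, T3 and T6. At T12 all earlier parameters are re-evaluated.

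**The concern.** The safety section treats the study dose as lying below the level at which it expects a bleeding-time effect. A weight-based rule without a maximum has that property only up to a certain weight, and nothing in the eligibility criteria keeps participants below it.

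The safety sentence can be read in two ways. As a description of the doses the study uses, it is untrue for a heavy enough participant. As an intended ceiling, it is missing from the text that staff would use to work out a dose, and nothing says which instruction prevails when the two conflict. Either way, someone who applies the dosing sentence exactly could give a heavy adolescent more than the safety section says is given.

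What is at stake is the safety of individual participants and the accuracy of a safety statement in a paediatric protocol. No endpoint, comparison or analysis depends on it.

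**Working it through.** **Inputs**

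- Dose rate: 60 mg/kg/day of EPA + DHA (Protocol, Supplementation; repeated as 60 mg/kg in Subjects and Methods and in the SAP).
- Threshold: 5 g/day = 5000 mg/day (Protocol, Study security and caution of the subject included).
- Capsule content: 400 + 200 = 600 mg, or 200 + 100 = 300 mg, of EPA + DHA (Protocol, Supplementation).
- Participant weights: not given in either document.

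**Step 1: reproduce the safety statement.** Daily dose in g = 60 × weight in kg / 1000.

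| Weight (kg) | Dose under the rule (g/day) | Below 5 g? |
|---|---|---|
| 20 | 1.2 | yes |
| 40 | 2.4 | yes |
| 60 | 3.6 | yes |
| 80 | 4.8 | yes |
| 83 | 4.98 | yes |
| 84 | 5.04 | no |
| 90 | 5.4 | no |
| 100 | 6.0 | no |

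The statement holds for lighter children but not for every eligible child.

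**Step 2: find the weight at which it fails.** 5000 mg / 60 mg/kg = 83.3 kg.

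**Step 3: translate to capsules.** The dose is 5400/600 = 9 large capsules at 90 kg and 6000/600 = 10 at 100 kg. Eight large capsules give 8 × 600 = 4800 mg, which is the exact dose at 4800/60 = 80 kg. The next step up is 4800 + 300 = 5100 mg with one small capsule, or 4800 + 600 = 5400 mg with one large one. If doses are rounded up to whole capsules, 5 g is therefore passed just above 80 kg.

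**Step 4: allow for what the 5 g counts.** The safety section's figure is for omega-3, whereas the rule counts only EPA + DHA. If the product also contains other omega-3, equal to a fraction f of its EPA + DHA, the crossover weight becomes 83.3/(1 + f) kg. The documents do not give f. With f = 0 the crossover is 83.3 kg. With f = 0.2/4.8 = 4.2% it is 5000/(60 × 1.042) = 80 kg. So 83.3 kg is the highest the crossover can be.

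**Step 5: effect of a cap at 4.8 g/day.** Doses are unchanged up to 80 kg. Above that, the dose per kg falls to 4800/90 = 53.3 mg/kg at 90 kg and 4800/100 = 48.0 mg/kg at 100 kg.

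**The case against.** The strongest reply is that the limit is already in the Protocol. It is a short document, and its dosing and safety sections can be read together as 60 mg/kg/day at doses under 5 g. On that reading the complaint is only that the limit is not repeated, and staff would exceed it only by ignoring the safety section. The translated English does not settle which meaning was intended.

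The hazard is also partly managed. Coagulation monitoring is required regardless of dose, it covers T0, T3, T6 and T12, and coagulation defects are excluded. This is a paediatric clinic, and nothing in the documents shows that any participant exceeds 83.3 kg. The T0 schedule also ties the start of supplementation to deficiency and willingness to take part, which narrows the group further. Finally, because the 5 g refers to omega-3, a cap of 4.8 g of EPA + DHA would not guarantee staying below it if the product contained about 4% or more of other omega-3.

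Much of this stands, and it is why the impact is small. It does not remove the gap. A limit that appears only in a clause explaining why blood is tested is easily missed by someone calculating a dose, and the descriptive reading is untrue above 83.3 kg. Monitoring does not replace a dose limit: the first scheduled test on treatment is at three months, and the documents state no action threshold or dose-reduction rule. Weights are unknown, but the children with onset in 2014 to 2016 are supplemented only later, so some are years past onset. The point about total omega-3 is fair. It bears on the choice of figure, not on the need for one.

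**Conclusion.** The concern holds. The dosing rule as written gives more than 5 g/day of EPA + DHA to any participant above 83.3 kg, contrary to the safety section. The excess is 0.4 g/day at 90 kg (5.4 − 5.0) and 1.0 g/day at 100 kg (6.0 − 5.0).

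The impact is minor but worth correcting. The arithmetic is certain. The number of children concerned is unknown and may be zero. The 83.3 kg figure assumes that only EPA + DHA count toward the 5 g and that doses are not rounded up to whole capsules; relaxing either assumption can only lower it.

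**What to change.** In the Supplementation section of the Protocol, add a limit beside the dose: 60 mg/kg/day of EPA + DHA, to a maximum below 5 g/day. Make the same addition in Subjects and Methods and in the SAP so that all three statements of the dose agree. The edit in Supplementation matters most.

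A practical example is 4.8 g/day, or eight 600 mg capsules. The clinical team should set the figure after checking the product's total omega-3 content, because 4.8 g of EPA + DHA stays below 5 g of omega-3 only if other omega-3 adds less than 0.2 g. It would also be good practice, as a separate matter, to record the daily dose actually given.

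The cost is one phrase in three places, with no change to design or analysis. The small drawback is the lower dose per kg above 80 kg set out in the working.
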